We require a minimum of 342 DMPA clients randomized to receive care from either the LHV or an LHW (1:1 allocation) for 90% power and 5% significance level to test the non-inferiority hypothesis that LHWs can screen potential DMPA clients for method initiation just as adequately as LHVs with a non-inferiority margin of 7.5%, assuming that both LHVs and LHWs perform at a 95% success rate. In Pakistan, there is usually at least one LHV assigned to a health facility and many more LHWs affiliated with and under the supervision of resident LHVs. Therefore, we will use a 3 to 1 ratio of LHWs to LHVs at each health facility in the trial.

For logistical reasons, we plan to obtain the full target sample size of 342 DMPA initiators from the 5 urban health facilities in Karachi to ensure that adequate analyses can be done with this group. We will recruit additional participants (~100) from 5 rural facilities in Thatta to help assess possible differences in performance between LHV and LHWs in rural and urban areas, but the expectation is that there will be no difference. LHWs undergo standardized training in Pakistan. If we can be comfortable that providers in rural and urban areas perform in similar manner, the overall sample size for the analysis may be pooled for an increase in power. The decision whether to pool the data or not will be made during the blind review of the data as described below.

Given the relationship between LHWs and LHV within clinics, we plan to account for the correlations of participant outcomes within providers and providers within clinics in the analysis. We expect that some of these correlations would lead to decreases in power and others to lead to increases in power for within clinic comparisons. Power calculations were not adjusted for these potential correlations as the net effect on power may be offset with each other.

V. General Analytic Considerations

A. Data Sources

A.1 Client exit interview

Client exit interviews measure the study's secondary outcomes of client satisfaction with the method and provider. The exit interview also provides additional information related to appropriate screening such as discussion of side effects, warning/danger signs, advantages and disadvantages of DMPA use with clients. The client exit interview includes questions on the following domains:

1. Sociodemographic characteristics
2. Experiences using contraceptive methods
3. Factors in her decision to use DMPA

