Even though the study is open labeled, the randomization was prepared by an independent randomization manager and data management is separated from the analysis team. Thus, the analysis team will initially be blinded to the group assignments. Unblinding of the analysis team will follow a three-step process: First, key decisions regarding the primary and secondary outcomes listed above will

be made blinded to study group assignment. These outcome variables will be constructed, checked for missing data, distributional anomalies or other problems, finalized and verified. Decisions about re-categorization, transformation, missing data, and final variable definition will be completed after initial descriptive analysis and prior to further analysis for the specific objectives. Descriptive analysis of the outcomes will be done by facility and rural/urban designation. This check will also include a check of protocol violations, such as randomization errors (this review will be coordinated between the data manager and the randomization manager to maintain blinding of the analysis team) to decide if any data should be excluded from the analysis. Primary analysis will be conducted based on the intent to treat (ITT) approach where all participants randomized will be analyzed in the study group to which they were randomized. During blind review, decisions will be made regarding any modification to the ITT principle for primary analysis and whether a per protocol analysis will be conducted as secondary or sensitivity analysis. Second, once these key decisions have been made, the randomization manager will provide a participant list with blinded study arm assignments to the analysis team. A descriptive bivariate analysis will be done using blinded treatment assignments stratified by rural/urban designation to assess whether pooling the data will be appropriate. A decision whether further analysis will be pooled or not will be done at this time. Partial blinding will be maintained until statistical conclusions regarding the primary outcome (screening outcome) and primary analysis have been made and verified. This will be based on the pooled data or on the urban data only depending on the decision made in the prior step. The analysis team will be fully unblinded for all remaining analysis.

E. Test Size and Confidence Levels

The type I error for the non-inferiority test and other performance outcomes will be set at the two-sided $\alpha=0.05$ significance level.

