VI. Analysis of Fieldwork Data

An analysis of fieldwork data will be presented. This will include the number of DMPA acceptors approached, included, and randomized to LHW or LHV care.

VII. Analysis of participant characteristics

A descriptive summary of DMPA user, LHV, and LHW characteristics will be presented by urban and rural setting. DMPA client characteristics will include age, marital status, education, number of children, desire for more children, and birth spacing plans. Provider characteristics will include age, marital status, education, years of service, and years of DMPA experience.

VIII. Analysis of Study Objectives

We plan to compare a series of indicators of the performance of LHWs compared to LHVs in the provision of injectable contraception services. Our primary outcome, appropriate screening, is a binary variable comprised of the gold standard nurse's assessment of client eligibility for DMPA compared with the LHV's or LHW's assessment of client eligibility. If the LHV's or LHW's assessment agrees with the gold standard nurse's assessment, the screening is deemed appropriate.

Analytical model

We will test the non-inferiority hypothesis that LHWs can screen potential DMPA clients for method initiation just as adequately as LHV with a non-inferiority margin of 7.5%. Given the relationship between LHWs and LHV within clinics, we will employ a generalized mixed model using a logit link to account for the correlations of participant outcomes within providers and providers within clinics. Random effects will be included for clinics and providers within clinic. The non-inferiority test will be conducted at a 5% significance level. A similar approach will be used to compare appropriate counseling. No covariate adjustments are planned for the primary analyses. However, exploratory analyses will include the following covariates: LHV/LHW age, marital status, education level, years of service, years of experience with DMPA, and average DMPA-IM injections given per month prior to the trial. Years of service, years of experience with DMPA, and average injections per month will be analyzed either as categorical or continuous variables based on exploratory analyses; either odds ratios or beta coefficients will be reported.

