As part of the blind analysis review, we will ascertain whether or not study outcomes differ for rural and urban sites. If they do not differ, as anticipated, we will combine the data from the five sites in Karachi with the five sites in Thatta. If differences are detected via descriptive analyses, we will present stratified results, but will be unable to test for significant differences as the trial was not powered for that purpose. In that event, the focus will be on the urban sites only, whose sample size (n=342) was powered to test the non-inferiority hypothesis.

Other comparisons between groups will be primarily descriptive to explore the differences in the provision of DMPA services and client satisfaction measures by each cadre of provider, by DMPA type and urban/rural setting if those data are not pooled. Similarly, objective and provider-perceived comparisons between injection techniques and injection characteristics, respectively, will be primarily descriptive and exploratory.

Analyses by Objective

Objective 1: *To assess whether LHWs can screen and initiate women on DMPA injections as safely and effectively as LHV.*

To answer this objective, the analysis will report the odds ratio of appropriate screening and counseling by LHWs compared with LHV using multi-level generalized mixed models as described above. The generalized linear mixed model accounts for the multilevel structure of the data (i.e., clinics and providers).

Objective 2: *Assess whether DMPA clients of Lady Health Workers and Lady Health Visitors are equally satisfied with their respective providers and the family planning services they provide.*

Descriptive analysis will be completed using indicators of client satisfaction and client-provider interactions for LHW and LHV clients.

Table 2: Summary of analysis approach and data sources for the primary and secondary outcomes

Outcome	Analysis	Stratified by	Source
Objective 1 Outcomes			
Screening for DMPA use	GLMM and descriptive	Cadre, urban/rural	Observation checklist of screening and gold-standard nurse's assessment
Counseling/Discussion of DMPA side effects, danger/warning signs, advantages and disadvantages	GLMM and descriptive	Cadre, urban/rural	Observation checklist of screening
Appropriate injection technique*	Descriptive	Cadre, urban/rural	Observation checklist for DMPA-IM, q1-q17; Observation checklist for DMPA-SP, q1-q22
Needle stick injuries*	Descriptive	Cadre, urban/rural	LHW/LHV questionnaire

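### The 7.5% non-inferiority margin fits a difference in proportions, but the only inferential result planned for the primary outcome is an odds ratio, with no stated test scale, odds-ratio bound or conversion.

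*SAP*

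**What the plan says.** SAP section IV (Sampling Design) sizes the trial "with a non-inferiority margin of 7.5%, assuming that both LHVs and LHWs perform at a 95% success rate", with 342 clients allocated 1:1, 90% power and a 5% significance level. Protocol section III (Sample size) says the same. Neither calls the margin absolute, relative or an odds ratio.

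SAP section VIII (Analytical model) plans to test that LHWs screen "just as adequately as LHV with a non-inferiority margin of 7.5" per cent, using a mixed model with a logit link: "Random effects will be included for clinics and providers within clinic". Protocol section IV (Data analysis) matches. Neither says on which scale the model result meets the margin.

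For Objective 1, SAP section VIII says "the analysis will report the odds ratio of appropriate screening and counseling by LHWs compared with LHV using multi-level generalized mixed models". Table 1 of the Objective 1 table shells has columns for an odds ratio, a confidence interval and a p-value, and its footnote ties the last two to the non-inferiority test. Table 4 shows counts and percentages by cadre, without a difference, an interval or a test.

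On the level, SAP section V.E says "The type I error for the non-inferiority test and other performance outcomes will be set at the two-sided" 0.05 level. The Table 1 shell has a 90% interval in its heading and a 95% interval in its footnote.

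**The concern.** A non-inferiority conclusion needs an estimate, a confidence limit and a bound, all on one scale. Here the bound appears to be in percentage points, while the only estimate with an interval is an odds ratio. The odds ratio equal to a 7.5-point loss depends on the LHV success rate, so the planned interval cannot be set against the margin without a further rule, and none is written.

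Screening is the only outcome the trial was powered for, and the result is meant to inform policy. If the scale is settled only at analysis, the same data could be called non-inferior on one scale and not on the other.

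**Working it through.** **Inputs.** From SAP section IV: success rate 95% in both cadres, margin m = 0.075, power 90%, 342 clients (171 per arm). If rural sites are pooled, 442 clients give 221 per arm. All calculations ignore clustering, as the plan's own calculation does.

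**1. Reproduce 342.** Difference in proportions, one-sided 5%:
- Farrington-Manning: n = [(z₀.₉₅·s₀ + z₀.₉₀·s₁)/m]². The restricted null rates are 96.83% and 89.33%, so s₀ = 0.3550, and s₁ = √(2 × 0.95 × 0.05) = 0.3082. Then n = [(1.645 × 0.3550 + 1.282 × 0.3082)/0.075]² = 170.4, so 171 per arm and 342 in total.
- Unpooled Wald: n = 2 × 0.95 × 0.05 × (1.645 + 1.282)²/0.075² = 144.6. With continuity correction, (144.6/4) × [1 + √(1 + 4/(144.6 × 0.075))]² = 170.3, again 342 in total. Without the correction it gives 290.
- Log odds ratio against the converted bound of 0.368 (step 2): n = [2/(0.95 × 0.05)] × (1.645 + 1.282)²/0.9985² = 361.6, so 724 in total.

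The stated figure therefore fits a difference in proportions at one-sided 5%. At one-sided 2.5% the two matching methods give 424 and 408.

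**2. Convert the margin.** For LHV rate q, the equivalent odds ratio is [(q − 0.075)/(1 − q + 0.075)] ÷ [q/(1 − q)].

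| LHV rate | Odds ratio equal to a 7.5-point loss | Loss allowed by a fixed 0.368 |
|---|---|---|
| 90% | 0.524 | 13.2 points |
| 95% | 7/19 = 0.368 | 7.5 points |
| 98% | 0.194 | 3.3 points |

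The mixed-model odds ratio is also conditional on the random effects. With an assumed total logit SD of 1, the 95% entry moves from 0.368 to 0.338.

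**3. Illustration at the planned rates.** No document proposes an odds-ratio bound; 0.368 is used only to show what the choice of scale is worth. At 171 per arm the log odds ratio has SE √[2/(0.0475 × 171)] = 0.496. Power is Φ(0.9985/0.496 − 1.645) = 64% (63% by enumerating all binomial results). On the difference it is 90% (Farrington-Manning) or 94% (Wald). Enumeration with Wald limits has the two scales disagreeing in 31% of results, nearly all passing on the difference and failing on the odds ratio. At 221 per arm they disagree in 25%.

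Example: LHW 160/171, LHV 163/171. The difference is −1.8 points with a 90% lower limit of −5.8, which is non-inferior. The odds ratio is 0.714 with a 90% lower limit of 0.325, below 0.368, so non-inferiority is not shown.

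**4. Illustration below the planned rates.** True loss exactly 7.5 points, 171 per arm, one-sided 5%, Wald:

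| LHV / LHW rate | Declared non-inferior, fixed 0.368 | Declared non-inferior, difference |
|---|---|---|
| 95% / 87.5% | 5% | 6% |
| 90% / 82.5% | 29% | 5% |
| 85% / 77.5% | 54% | 5% |

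**5. Confidence level.** One-sided 5% corresponds to a 90% interval. If the lower limit of a 95% interval decides, power at 171 per arm is Φ[(0.075 × √171 − 1.960 × 0.3550)/0.3082] = 82% (Farrington-Manning), or 83% with continuity-corrected Wald.

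**The case against.** The strongest reply is that this is missing wording and not a contradiction. The outcomes are proportions, the margin stands beside a 95% success rate, 342 reproduces on the difference, and a logit model can yield a marginal difference. An analyst who tested that difference would comply with both documents, and no harm would follow. All of this stands. A reader might infer that the plan rules out a difference-scale test; the text does not support that. The step is unwritten, and the result the SAP does specify cannot do the job alone.

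A reader might also infer that the trial as planned has only about 64% power, or a 29% false-positive rate. Neither follows, because those figures depend on a bound that no document proposes. Nor can the danger be described as lost power only: that holds at the planned 95%, and the error turns the other way if LHVs perform below it.

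Blinding is a partial answer. The SAP says "Partial blinding will be maintained until statistical conclusions regarding the primary outcome (screening outcome) and primary analysis have been made and verified". That limits steering towards a preferred result, but it supplies no rule, and the scale of the test is not among the decisions assigned to the blind review.

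Finally, a justified, pre-specified odds-ratio bound would also be a valid repair. It would be tied to an assumed LHV rate, and at 0.368 would need 724 clients for 90% power.

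**Conclusion.** The concern holds as a gap in the decision rule for the only powered hypothesis. That the margin is absolute is an inference, resting on the reproduction of 342 under two standard methods at one-sided 5%. Given that, the planned odds-ratio interval cannot decide the test, because the equivalent bound runs from 0.524 to 0.194 as the LHV rate goes from 90% to 98%.

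The power, disagreement and error figures show what the choice of scale is worth under one hypothetical bound, with independent observations. They are not properties of the written plan.

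The same output carries an inconsistent level: 342 with 90% power needs one-sided 5%, whereas two-sided 0.05 with a 95% interval gives about 82-83% before clustering.

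**What to change.** Keep the logit mixed model with clinic and provider effects, and amend the SAP before arm codes are released:

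- **Estimate and rule (section VIII).** Make the primary estimate the LHW-minus-LHV difference in marginal probabilities of appropriate screening from that model, with its confidence interval. Declare non-inferiority only if the lower limit exceeds −7.5 points. Define the p-value as the test of H₀: difference ≤ −7.5 points.
- **Table 1 shell.** Add the two proportions, the difference and its interval. Keep the odds ratio as supplementary.
- **Level (sections V.E and VIII, Table 1 shell).** State one level throughout. A 90% interval (one-sided 5%) matches 342. If a 95% interval is kept, restate power at 342 as about 82-83% before clustering.
- **Interval method.** Fix it in advance, allowing for the small number of facilities. If the data are not pooled, "the focus will be on the urban sites only, whose sample size (n=342) was powered to test the non-inferiority hypothesis", which means five facilities. Statisticians would differ on the small-sample correction, so that choice is left to the sponsor's statistician.

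The cost is SAP wording, one table shell and a few lines of post-estimation code, with no new data. The downside is a less favourable stated power if the 95% interval is kept or a small-sample correction is used.

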IRBNET# 1035709: A randomized controlled trial of safety and effectiveness of Depo Provera intramuscular and subcutaneous administration comparing lay Lady Health Workers with clinically-trained Lady Health Visitors in Pakistan

STATISTICAL ANALYSIS PLAN

This statistical analysis plan gives a detailed explanation of the data analysis summary included in the study protocol.

I. Study Objectives

The goal of this evaluation is to assess whether the community health worker cadre, Lady Health Workers (LHWs) in Pakistan can screen and initiate women on intramuscular (IM) and subcutaneous Depo Provera injections as safely and effectively as their clinically-trained counterparts, Lady Health Visitors (LHV). Although LHWs are already allowed to provide follow-up doses in the community, this RCT will focus on the comparison of safety and effectiveness of screening, counseling and administration of DMPA IM and the subcutaneous injection, Sayana Press® (SP).

The study's primary outcomes are:

- Proportion of Lady Health Workers and Lady Health Visitors that appropriately screen women for DMPA use;
- Proportion of Lady Health Worker and Lady Health Visitor clients that report discussion with their respective providers on side effects, danger signs, advantages and disadvantages of DMPA use;
- Proportion of Lady Health Workers and Lady Health Visitors that demonstrate appropriate injection technique
- Proportion of Lady Health Workers and Lady Health Visitors that report needle stick injuries;
- Proportion of Lady Health Workers that properly maintains a client (re)injection log.

A secondary objective is to assess whether the clients of LHWs and LHV are equally satisfied with their respective providers and the family planning services they provide.

The study's secondary outcomes are:

- Satisfaction with the method;
- Satisfaction with the services received from the provider;
- Reports of client ability to speak freely and ask questions of provider;
- Friendly and respectful behavior toward client.

II. Study Design

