Use of client (re)injection log*	Descriptive	urban/rural	LHW/LHV questionnaire, qLHW6
Objective 2 Outcomes			
Client satisfaction with DMPA*	Descriptive	Cadre, DMPA type	Client exit interview, q313
Client satisfaction with service delivery*	Descriptive	Cadre, DMPA type	Client exit interview, q318
Client comfort asking provider questions*	Descriptive	Cadre, DMPA type	Client exit interview, q303
Friendly and respectful behavior by provider*	Descriptive	Cadre, DMPA type	Client exit interview, q301

* If the data are pooled, there will be no urban/rural stratification

Objective 1 Table Shells: Screening and counseling for DMPA

Table 1: Odds of appropriate screening and counseling for DMPA initiation by Lady Health Workers compared with Lady Health Visitors in Pakistan

OR	90%CI	p-value
Appropriate screening		
Appropriate counseling		

Appropriate screening defined as agreement between the provider and independent assessment by a gold standard nurse
Appropriate counseling defined as having discussed side effects, warning/danger signs, advantages, and disadvantages of DMPA

95% CI and p-value reported for test of non-inferiority

Table 2: Exploratory analysis of factors affecting appropriate screening for DMPA initiation by Lady Health Workers compared with Lady Health Visitors in Pakistan

	N (%)	OR (or β)	95%CI	p-value
Age				
Age cat 1				
Age cat 2				
Etc.				
Marital status				
Marital status 1				
Marital status 2				
Etc.				
Education level				
Education level 1				
Education level 2				
Etc.				
Years of service				
Categorical or continuous TBD				
Years of DMPA experience				
Categorical or continuous TBD				
Avg. DMPA injections/month				
Categorical or continuous TBD				

Appropriate screening defined as agreement between the provider and independent assessment by a gold standard nurse

Table 3: Exploratory analysis of factors affecting appropriate counseling for DMPA initiation by Lady Health Workers compared with Lady Health Visitors in Pakistan

	N (%)	OR (or β)	95%CI	p-value
Age				
Age cat 1				
Age cat 2				
Etc.				
Marital status				
Marital status 1				
Marital status 2				
Etc.				
Education level				
Education level 1				
Education level 2				
Etc.				
Years of service				
Categorical or continuous TBD				
Years of DMPA experience				
Categorical or continuous TBD				
Avg. DMPA injections/month				
Categorical or continuous TBD				

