Appropriate counseling defined as having discussed side effects, warning/danger signs, advantages, and disadvantages of DMPA				

Table 4: Comparison of Lady Health Workers and Lady Health Visitors on DMPA service delivery indicators (n, %)

	Urban	Rural		
	LHW	LHV	LHW	LHV
Appropriate screening				
Appropriate counseling				
side effects				
danger signs				
advantages/disadvantages				
Appropriate injection technique				
Needle stick injuries				
Client log maintained				

Objective 2: Client Satisfaction and Client-Provider Interaction

Table 5: Exemplar of Client Satisfaction and Client-Provider Interaction items (n, %)

	LHW		LHV	
	SP	IM	SP	IM
Satisfaction with method				
very satisfied				
somewhat satisfied				
not satisfied				
Satisfaction with services				
very satisfied				
somewhat satisfied				
not satisfied				
Satisfaction with provider				
very satisfied				
somewhat satisfied				
not satisfied				
Comfort asking questions				
yes				
no				

Figure 1: Graphic presentation of observation checklist for screening

Observation Checklist to Evaluate Providers Who Screen Clients for Initial DMPA Use

Type of provider being observed: Lady Health Worker
Lady Health Visitor

Please record the response given to the provider by the client for the following items. If the provider does not ask the question, please draw a line through the item.

NO	1. Have you ever been told you have breast cancer?	YES
NO	2. Have you ever had a stroke or heart attack, or do you currently have a blood clot in your legs or lungs?	YES
NO	3. Do you have a serious liver disease or jaundice (yellow skin or eyes)?	YES
NO	4. Have you ever been told you have diabetes (high sugar in your blood)?	YES
NO	5. Have you ever been told you have high blood pressure?	YES
NO	6. Do you have bleeding between menstrual periods, which is unusual for you, or bleeding after intercourse (sex)?	YES
NO	7. Have you ever been told that you have a rheumatic disease such as lupus?	YES
NO	8. Do you have two or more conditions that could increase your chances of a heart attack or stroke, such as smoking, obesity, high blood pressure, or diabetes?	YES
NO	9. Are you currently breastfeeding a baby less than 6 weeks old?	YES

If the client answered NO to *all of questions 1–9*, did the provider tell her she is a good candidate for DMPA?
Yes No
Did provider proceed to questions 10–15?
Yes No

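### Objective 2 asks whether LHW and LHV clients are equally satisfied, but the SAP specifies no overall cadre difference, interval, margin or allowance for clustering

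*SAP*

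**What the plan says.** SAP section I gives the secondary objective as "to assess whether the clients of LHWs and LHV are equally satisfied with their respective providers and the family planning services they provide". The protocol words it the same way in the Study Summary and in section II.

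The analysis is set out in SAP section VIII, Analyses by Objective, Objective 2, in one sentence: "Descriptive analysis will be completed using indicators of client satisfaction and client-provider interactions for LHW and LHV clients". Earlier in section VIII the SAP says: "Other comparisons between groups will be primarily descriptive to explore the differences in the provision of DMPA services and client satisfaction measures", by cadre, by DMPA type, and by setting if the data are not pooled. The SAP's summary Table 2 marks all four Objective 2 outcomes (for example "Client satisfaction with service delivery") as descriptive, stratified by cadre and DMPA type.

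The only shell for this objective is Table 5. It is labelled an exemplar and shows n and % in four columns: LHW-SP, LHW-IM, LHV-SP and LHV-IM. It has no column for a cadre total, a difference, an interval or a p-value.

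By contrast, screening has a mixed model with random effects for clinic and for provider within clinic. For counseling the SAP adds: "A similar approach will be used to compare appropriate counseling". The 7.5% margin is set for screening alone.

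**The concern.** The objective is a question about cadre, and its wording invites an answer of yes, equal. A table of percentages does not show how large a cadre gap is still compatible with the data. Two similar percentages may reflect real similarity or simply too few clients to tell.

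Two features add to this. First, the shell divides each cadre by product, so any comparison read straight from it uses about half the clients behind the overall cadre comparison. Second, clients are nested in a small number of providers, and opinions of a provider are likely to be correlated among her clients. The SAP recognises this correlation in section IV and models it for screening and counseling, but plans nothing for satisfaction.

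The protocol's section V says the findings will inform policy dialogue and possible scale-up. An unsupported statement that clients were equally satisfied could be taken at face value there.

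**Working it through.** **The plan's own figure.** The documents state one sample size, a minimum of 342 (171 per arm), for the screening test: 95% success in both cadres, margin 7.5 points, 90% power. With one-sided 5%, n = 2 × 0.95 × 0.05 × (1.645 + 1.282)² / 0.075² = 144.6 per arm. The continuity correction, n/4 × (1 + √(1 + 4/(n × 0.075)))², gives 170.3, so 171 per arm and 342 in all. The figure is reproduced, but it concerns screening. Neither document gives power, precision or a margin for satisfaction.

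**Inputs for satisfaction.**
- Urban: 342 clients, 1:1 by cadre, so 171 per arm (SAP section IV).
- Pooled: about 442 (SAP Table 1 of eligibility criteria; protocol, Sample size), so about 221 per arm.
- Product: the protocol (Randomization procedures) describes the second randomization as identical to the first. Taken as 1:1, that gives about 85 per cell urban and 110 pooled.
- Providers: one LHV and three LHWs per facility, so 5 and 15 in urban sites, 10 and 30 overall.
- Proportion satisfied: not in the documents; assumed 80%, 90% or 95%.
- Provider intraclass correlation: not in the documents; assumed 0 or 0.05.

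**Without clustering.** Half-width = 1.96 × √(2p(1−p)/n). Example, p = 0.90 and n = 171: 1.96 × √(0.18/171) = 6.4 points.

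**With provider clustering.** Each arm's variance is multiplied by 1 + (m − 1) × ICC, with m the mean clients per provider. Urban, m = 171/5 = 34.2 for LHVs and 171/15 = 11.4 for LHWs. At ICC 0.05 the factors are 1 + 33.2 × 0.05 = 2.66 and 1 + 10.4 × 0.05 = 1.52. At p = 0.90: 1.96 × √(0.09/171 × (2.66 + 1.52)) = 9.2 points. Pooled, m = 22.1 and about 7.4, treating providers as equally loaded.

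| 95% half-width, points, at 80/90/95% satisfied | Urban | Pooled |
|---|---|---|
| Overall cadre difference, no clustering | 8.5 / 6.4 / 4.6 | 7.5 / 5.6 / 4.1 |
| Cadre difference within one product, no clustering | 12.0 / 9.0 / 6.5 | 10.5 / 7.9 / 5.7 |
| Overall cadre difference, ICC 0.05 | 12.3 / 9.2 / 6.7 | 9.7 / 7.3 / 5.3 |

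Reading within a product widens the uncertainty by √2, about 1.41. Even if the two cadre percentages coincided exactly, true gaps up to the half-width would remain compatible with the data.

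**Would an equivalence test do better?** For illustration only, borrow the 7.5-point screening margin and use two one-sided 5% tests without clustering: power = 2Φ(0.075/SE − 1.645) − 1, or zero if that is negative. With truly equal rates this gives 7/50/88% urban and 26/67/95% pooled. At the lower rates, a formal claim of equivalence would usually fail even if it were true.

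**The case against.** The strongest reply is that the SAP openly calls this analysis descriptive, consistent with the protocol's Data analysis section, and sets no equality test or decision rule for satisfaction. That is correct. A reader might infer that the plan intends to declare equality; the documents do not say so. The mismatch is between the wording of the objective and what the analysis can answer, and it concerns a secondary objective.

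A reader might also infer that the cadre comparison is never shown. The documents do not support that either. Table 5 is only an exemplar: it omits the friendly-behavior item and adds a provider-satisfaction item that the summary Table 2 does not list. Section VIII plans description by cadre, and the cells carry counts, so SP and IM can be added. What remains missing is a specified difference with an interval that allows for clustering.

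Nor is the product split an oversight. The protocol's Overview and SAP section II say the product comparisons focus on acceptability of and satisfaction with the method. The split has less to offer for comfort asking questions or satisfaction with the provider.

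Section V.E might be thought to cover satisfaction: "The type I error for the non-inferiority test and other performance outcomes will be set at the two-sided" 5% level. Satisfaction is not named there, and the summary Table 2 gives it no test.

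Finally, pooling is the expected case, so urban-only figures would overstate the imprecision. Both are shown above.

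**Conclusion.** The point stands as a gap between objective and analysis. The plan would produce cadre percentages, but nothing that says how large a satisfaction gap the data leave open, so it cannot support a conclusion that the two groups are equally satisfied. Over the assumed range (80 to 95% satisfied, ICC 0 to 0.05, urban or pooled), the overall cadre difference would be known to within about 4 to 12 points.

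These sizes rest on assumed satisfaction rates and ICC. The clustered figures allow for provider correlation only. They also treat every randomized client as interviewed. Under the protocol's Client exit interview section the interview follows the first dose, so women found ineligible contribute nothing. The comparison is among treated and interviewed clients, and the numbers may be somewhat smaller.

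Adding an interval would not in itself establish equality, since that also needs a margin set in advance. It would let the report state what has been ruled out. The primary screening test is unaffected.

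**What to change.** 1. Add LHW-total and LHV-total columns to Table 5. Keep the SP/IM split as exploratory.
2. Fix the dichotomy of each multi-level item (for example, very satisfied against the rest) at the blind review. SAP section V.D already schedules recategorization of secondary outcomes there.
3. For each item report the LHW minus LHV difference in percentage points with a 95% CI that allows for provider and clinic clustering. The SAP's logit mixed model yields odds ratios, so state the route to a difference, for example a marginal risk difference standardised from that model. Name a fallback, such as a cluster-robust risk difference, if near-ceiling responses prevent convergence.
4. Define the analysis set as clients who completed the exit interview, and show by cadre how many were randomized but not interviewed.
5. State the conclusion as the range of differences the interval excludes, not as equal satisfaction. Alternatively, reword the objective as estimating the cadre difference.

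The cost is some SAP wording, two columns, a few extra model runs and a less absolute conclusion. No new data are needed.
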